7.3. Variables

The described variables are classified into two variable groups according to the role, the clinical outcome and baseline (demographic, clinical, treatment variables). The latter include the possible subgroups to consider. These analyses are initially exploratory to the extent that the specific analyses may be performed according to the sample collected.

Table 1. Table of Variables

Variable	Role	Data source (s)	Operational definition
Age	Demographic characteristic	Medical record	Birthday
Gender	Demographic characteristic	Medical record	Male, female, other
Race	Demographic characteristic	Medical record	White, half-breed, indigenous, black, others
Weight	Demographic characteristic	Medical record	Kg
Height	Demographic characteristic	Medical record	Mt (meters)
Body mass index	Demographic characteristic	Medical record	Kg/mt ²
City of residence	Demographic characteristic	Medical record	Cities of Colombia
Time to diagnosis to NVAF	Clinical characteristic	Medical record	Date (dd/mm/yy)
High alcohol intake at OAC prescription date	Clinical characteristic	Medical record	Yes, No

Variable	Role	Data source (s)	Operational definition
Diabetes	Clinical characteristic	Medical record	No, without chronic complication, with end-organ damage
Liver disease	Clinical characteristic	Medical record	No, mild, moderate, severe
Hypertension	Clinical characteristic	Medical record	Diagnosis of hypertension (Yes, No)
Uncontrolled hypertension at OAC prescription date	Clinical characteristic	Medical record	Yes, No
Rheumatic disease	Clinical characteristic	Medical record	Yes, No
Acquired Immune Deficiency Syndrome (AIDS)	Clinical characteristic	Medical record	Yes, No
Severe renal disease (dialysis, organ transplant)	Clinical characteristic	Medical record	Yes, No
Moderate renal disease (creatinine > 3 mg/dL)	Clinical characteristic	Medical record	Yes, No
Chronic heart failure	Clinical characteristic	Medical record	Yes, No
Myocardial infarction	Clinical characteristic	Medical record	Yes, No
Chronic obstructive pulmonary disease (COPD)	Clinical characteristic	Medical record	Yes, No
Peripheral vascular disease	Clinical characteristic	Medical record	Yes, No
Stroke or transient ischemic attack (TIA)	Clinical characteristic	Medical record	Yes, No
Dementia	Clinical characteristic	Medical record	Yes, No
Hemiplegia	Clinical characteristic	Medical record	Yes, No
Connective tissue disease	Clinical characteristic	Medical record	Yes, No
Leukemia	Clinical characteristic	Medical record	Yes, No

PFIZER CONFIDENTIAL

Variable	Role	Data source (s)	Operational definition
Malignant lymphoma	Clinical characteristic	Medical record	Yes, No
Peptic ulcer disease	Clinical characteristic	Medical record	Yes, No
Metastatic solid tumor	Clinical characteristic	Medical record	Yes, No
History of ischemic or hemorrhagic stroke	Clinical characteristic	Medical record	Yes, No
History of TIA	Clinical characteristic	Medical record	Yes, No
History of de tromboembolismo	Clinical characteristic	Medical record	Yes, No
Enfermedad coronaria	Clinical characteristic	Medical record	Yes, No
History of de hemorragia gastrointestinal	Clinical characteristic	Medical record	Yes, No
History of Intracranial bleeding	Clinical characteristic	Medical record	Yes, No
History of Other bleeding	Clinical characteristic	Medical record	Yes, No
Bleeding history or predisposition at start OAC treatment	Clinical characteristic	Medical record	Yes, No
INR > 60% at start OAC treatment	Clinical characteristic	Medical record	Yes, No
Use of aspirin at start OAC treatment	Clinical characteristic	Medical record	Yes, No
Use of clopidogrel at start OAC treatment	Clinical characteristic	Medical record	Yes, No
Use of NSAIDs at start OAC treatment	Clinical characteristic	Medical record	Yes, No
HASBLED at start OAC treatment	Clinical characteristic	Medical record	Score – number higher than 0
CHA2DS2-VASc at start OAC treatment	Clinical characteristic	Medical record	Score – number higher than 0
Anaemia at start OAC treatment	Clinical characteristic	Medical record	Yes, No
Stroke	Clinical outcome	Medical record	Yes, No
Time to stroke	Clinical outcome	Medical record	Date of event dd/mm/yy

Pfizer Confidential

Variable	Role	Data source (s)	Operational definition
Type of stroke	Clinical outcome	Medical record	Ischemic stroke, Haemorrhagic or not specified
Pulmonary embolism	Clinical outcome	Medical record	Yes, No
Time to pulmonary embolism	Clinical outcome	Medical record	Date of event dd/mm/yy
Gastrointestinal bleeding	Clinical outcome	Medical record	Yes, No
Time to gastrointestinal bleeding	Clinical outcome	Medical record	Date of event dd/mm/yy
Intracranial bleeding	Clinical outcome	Medical record	Yes, No
Time to Intracranial bleeding	Clinical outcome	Medical record	Date of event dd/mm/yy
Other major bleeding	Clinical outcome	Medical record	Yes, No
Time to other major bleeding	Clinical outcome	Medical record	Date of event dd/mm/yy
CCI			
Persistence	Clinical outcome	Claim databases	Yes, No
OAC treatment	Treatment	Claim databases	Warfarin, apixaban, rivaroxaban, dabigatran
Diagnosis at index date	Treatment	Claim databases	Diagnosis AF based on ICD-10
Date of OAC prescription	Treatment	Claim databases	Date reported dd/mm/yy
Dosage of the initial OAC treatment	Treatment	Claim databases	Mg per dose
Initial frequency of OAC treatment	Treatment	Claim databases	Number of doses at initial OAC treatment
OAC escalation	Treatment	Claim databases	Yes, No
Type of OAC escalation	Treatment	Claim databases	Dose increase or dose decrease
Time to OAC escalation	Treatment	Claim databases	Date reported dd/mm/yy
CCI			

Variable	Role	Data source (s)	Operational definition
CCI			
INR testing monthly in patients with warfarin	Treatment	Medical record	INR reported in the medical record per month
Switch to another OAC treatment:	Treatment	Claim databases	Yes, No
Time to Switch to another OAC treatment	Treatment	Claim databases	Date reported dd/mm/yy
Causa de cambio	Treatment	Medical record	Adverse events, effectiveness, adherence, patient preference, administrative problems, not reported, others
Concomitant therapies by OAC prescription	Treatment	Medical record	NSAIDs, Angiotensin-converting-enzyme (ACE) inhibitors, Amiodarone, Beta-blockers, Angiotensin II receptor blockers (ARBs), Aspirin, Clopidogrel, Digoxin, Diuretics, calcium blockers, statins, proton pump inhibitor, selective H2 antagonists, antidiabetics, insulin, serotonin reuptake inhibitors
Previously exposed to warfarin	Treatment	Claim databases	Yes, No

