 - Pregnancy during the study period. ICD-10 O00-O9A
 - Diagnosis of venous thromboembolism (VTE) – ICD-10 codes: I26, I80 - I82;
- Individuals with a transitory diagnosis of NVAF prior to the use of the treatments of interest or index date;
- Exposure to more than one OAC on or after the index date, during the follow-up period;
- NOAC doses different from those recommended by the manufacturing laboratories.

Data Collection:

PFIZER CONFIDENTIAL

The information will be analyzed in two moments: (i) the period of the index date, where the baseline information of patients will be collected; (ii) and the follow-up period, during this period the clinical results will be evaluated as well as the continuation of the treatment in the study population and for specific subpopulations.

Variables:

- Clinical and demographic characteristics
- Treatment patterns (OAC usage, dose, concomitant medications, persistence)

Effectiveness outcomes:

- First CCI switch of treatment, first event of stroke/ systemic embolism

Safety outcomes:

- Major bleeding

C
C

Data sources:

The information will be used in the study comes exclusively from secondary sources.

- Claim database:
 - The persistence on therapy and treatment patterns (duration of treatment, changes, persistence), pharmacy claim information, demographic information, diagnosis and insurance data.
- Medical records:
 - Baseline demographic and clinical characteristics and the information related to the outcomes of interest (stroke/systemic embolism, bleeding events and death)

Statistic analysis

This type of analysis is descriptive and explanatory, as it depends largely on the sample size. Continuous variables will be presented as means, standard deviation or other measures of central tendency or position, while categorical variables will be presented as frequencies and percentages.

Regarding bivariate analyses of continuous variables with normal behavior, the Student's t test will be performed. In case of presenting non-normal behavior, the Mann-Withney test will be used. For variables that are continuous with several categories, analysis of variance (ANOVA) will be assessed. In the event of presenting a non-normal behavior, the multivariate analysis of variance (MANOVA) test will be carried out. For categorical variables, the χ^2 test will be used.

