6. RESEARCH QUESTION AND OBJECTIVES

Primary Objectives

- To assess demographic and clinical characteristics of NVAF patients treated with oral anticoagulants (OACs) in Colombia.
- To describe treatment patterns (eg. OAC usage, dose, concomitant medications, persistence)

Exploratory Objectives

- To descriptively assess the time to clinical events (Effectiveness and Safety Outcomes) among patients persistent on OAC therapy.

Effectiveness outcomes: First Stroke/ Systemic Embolism; CCI

Safety outcomes: Major bleeding, CCI

[figure not shown]

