7.2.2. Exclusion Criteria

Patients meeting any of the following criteria will not be included in the study:

- e) Patients with any of the following diagnoses prior to the use of the treatments of interest or index date:
 - Valvular heart disease or valve replacement – ICD-10 codes: I05, I06, I07, I08, I09, I22, I34, I35, I36, I37, I38, I39, I700, I702-I709; Q22, Q23, Q25, T82,Z95.
 - Pregnancy during the study period. ICD-10 O00-O9A
 - Diagnosis of venous thromboembolism (VTE) – ICD-10 codes: I26, I80 - I82;
- f) Individuals with a transitory diagnosis of NVAF prior to the use of the treatments of interest or index date;
- g) Exposure to more than one OAC on or after the index date, during the follow-up period.
- h) NOAC doses different from those recommended by the manufacturing laboratories.

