K272	Acute with both haemorrhage and perforation
K274	Chronic or unspecified with haemorrhage
K276	Chronic or unspecified with both haemorrhage and perforation
K280	Acute with haemorrhage
K282	Acute with both haemorrhage and perforation
K284	Chronic or unspecified with haemorrhage
K286	Chronic or unspecified with both haemorrhage and perforation
K290	Acute haemorrhagic gastritis
K625	Haemorrhage of anus and rectum
K920	Haematemesis
K921	Melaena
K922	Gastro-intestinal haemorrhage, unspecified
D62	Acute posthaemorrhagic anaemia
H356	Retinal haemorrhage
H431	Vitreous haemorrhage
H450	Vitreous haemorrhage in diseases classified elsewhere
H922	Otorrhagia
I312	Haemopericardium, not elsewhere classified
J942	Haemothorax
R04	Haemorrhage from respiratory passages
K661	Haemoperitoneum
M250	Haemarthrosis
N02	Recurrent and persistent haematuria
N938	Other specified abnormal uterine and vaginal bleeding
N939	Abnormal uterine and vaginal bleeding, unspecified
N950	Postmenopausal bleeding
R31	Unspecified haematuria
R58	Haemorrhage, not elsewhere classified
T792	Traumatic secondary and recurrent haemorrhage

- Ischemic stroke:** Patients who report the following diagnoses in the medical history during the follow-up period:

ICD-10	Description
I63	Cerebral infarction
I64	Stroke, not specified as haemorrhage or infarction

Except I63.6 Cerebral infarction due to thrombosis of cerebral veins, non-pyogenic

- Hemorrhagic stroke:** Patients presenting the following diagnosis in the medical record:

PFIZER CONFIDENTIAL

ICD-10	Description
I60	Subarachnoid haemorrhage
I61	Intracerebral haemorrhage
I62	Other nontraumatic intracranial haemorrhage

- **Systemic embolism:** Patients who report any of the following diagnoses:

ICD-10	Description
I74	Arterial embolism and thrombosis

Definition of covariates

- **Age:** Categorical variable, continues in years. It will be defined from the index date and will be used to assign patients to the following age categories:

18 - 49
 50 - 59
 60 - 69
 70 - 79
 ≥ 80 years old.

- **Charlson Index:** Charlson comorbidity index will be created during the reference period taking into account the following score:

1 point each:

- *Myocardial infarction*

ICD-10	Description
I21	Acute myocardial infarction
I22	Subsequent myocardial infarction
I252	Old myocardial infarction

- *Congestive heart failure*

ICD-10	Description
I110	Hypertensive heart disease with (congestive) heart failure

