7.7 Data Analysis

This type of analysis is descriptive and explanatory, as it depends largely on the sample size. Continuous variables will be presented as means, standard deviation or other measures of central tendency or position, while categorical variables will be presented as frequencies and percentages.

Regarding bivariate analyses of continuous variables with normal behavior, the Student's t test will be performed. In case of presenting non-normal behavior, the Mann-Withney test will be used. For variables that are continuous with several categories, analysis of variance (ANOVA) will be assessed. In the event of presenting a non-normal behavior, the multivariate analysis of

variance (MANOVA) test will be carried out. For categorical variables, the X² test will be used.

Exploratory analyses based on sample size:

The cumulative incidence of clinical outcomes (Stroke/ systemic embolism and major bleeding) will be calculated throughout the study period, from which the incidence or survival curves will be derived using the Kaplan Meier method. Incidence of events will be explored in clinically relevant subgroups based on sample size.

For the execution of the analysis, CCI and change of treatment, and missing treatments are considered as censures. Treatment comparison will be not conducted.

A similar analysis will be performed for the group of patients who have not presented stroke/ systemic embolism or major bleeding events to estimate the time for CCI change of treatment.

In the independent variables, the significance will be analyzed, as a level of statistical significance p < 0.05.

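### No visible Table 1 field captures systemic embolism (I74) or its date, although the stroke/systemic embolism outcome needs both

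*Combined protocol and SAP*

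**What the plan says.** The exploratory objective in section 6 names "First Stroke/ Systemic Embolism" as an effectiveness outcome; a further item is redacted. Section 7.1 ends a patient's follow-up at that event, among others. Section 7.3.1 defines systemic embolism by a single ICD-10 category, I74, "Arterial embolism and thrombosis". Section 7.7 then states: "The cumulative incidence of clinical outcomes (Stroke/ systemic embolism and major bleeding) will be calculated throughout the study period", with Kaplan-Meier curves to follow.

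Table 1 in section 7.3 lists the variables. Its visible clinical-outcome rows are:

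- stroke, its date, and its type ("Ischemic stroke, Haemorrhagic or not specified");
- pulmonary embolism, yes or no, and "Time to pulmonary embolism";
- gastrointestinal, intracranial and other major bleeding, each with a date;
- a redacted block;
- persistence.

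The two descriptions of the medical record as a data source differ. The abstract says that it supplies "the information related to the outcomes of interest (stroke/systemic embolism, bleeding events and death". Section 7.4.2 names stroke and bleeding only.

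**The concern.** A first stroke/systemic embolism outcome needs four items per patient: stroke, its date, systemic embolism, and its date. The visible table supplies the first two. Where the other two would be expected, directly after the stroke rows, it lists pulmonary embolism. In this plan that is a different diagnosis with a different code.

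The table matters because section 7.6.1 sets the electronic case report variables from the protocol and keeps the abstracting physicians unaware of the study objective. They cannot be expected to infer that arterial emboli are wanted if the form asks about pulmonary embolism. An event for which there is no field is also not a missing value: the patient appears event-free. The observed-case rule in section 7.7.1 would neither reveal nor repair this.

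**Working it through.** The plan states no figure to reproduce. The check compares what each section needs with what Table 1 visibly provides.

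| Place in the protocol | What it needs or provides |
|---|---|
| Section 6, objectives | Time to first stroke/systemic embolism |
| Section 7.1, follow-up | Date of first stroke/systemic embolism, as one end of follow-up |
| Section 7.3.1, definition | Systemic embolism = I74 |
| Section 7.7, analysis | Cumulative incidence of stroke/systemic embolism; also a group free of that outcome and of major bleeding |
| Section 7.3, Table 1 | Stroke and date: visible. Systemic embolism and date: not visible. Pulmonary embolism and date: visible |
| Section 7.3.1, Table 2 | I74, but as a baseline variable or possible confounder |
| Section 7.2.2, exclusions | "Diagnosis of venous thromboembolism (VTE) – ICD-10 codes: I26, I80 - I82", before treatment or the index date |
| Section 7.4.2, medical record | Stroke and bleeding; systemic embolism not named |

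**Step 1: do the codes overlap?** The exclusion list places I26 with venous thromboembolism, and the vascular component of CHA2DS2-VASc labels I26 as pulmonary embolism. Systemic embolism is I74 alone. The two sets share no code, so the pulmonary embolism fields cannot stand in for systemic embolism.

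**Step 2: what can be built from the visible fields?** Either stroke alone, which omits I74 events, or stroke plus pulmonary embolism, which is a different endpoint. Neither is the outcome that section 7.7 analyses.

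**Step 3: what does an unrecorded I74 event do?**

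- The composite loses an event, and the patient stays in the risk set after the date on which section 7.1 would have ended follow-up. Both effects push the estimated incidence down.
- A later stroke in that patient would be dated as the first composite event, and a later bleed would count although follow-up should have ended.
- The patient may be placed wrongly in the event-free group used for time to change of treatment.

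**Step 4: size.** The documents give no event rates. Suppose that a share s of first composite events are I74 events, and that none is recorded. Of 100 true first events, 100 × (1 − s) are captured at their proper date. With s = 5% that is 95; with s = 15% it is 85. The 5% to 15% range is an assumption and has no source in the documents. The mismatch does not depend on it.

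**The case against.** The strongest reply is that the table cannot be read in full. A redacted block of unknown length sits between the last bleeding row and persistence, and redacted content is not missing content. A systemic embolism field could be there. This stands as a limit on what can be claimed. It is unlikely, because the term is printed openly in the objectives, follow-up rule, definitions, Table 2 and analysis. Other items fit the block at least as well: death ends follow-up and is a medical-record outcome in the abstract, yet it has no visible row either.

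Secondly, the collection form need not copy Table 1. Section 7.6.1 ties the form to the protocol as a whole, which includes the I74 definition, and adds validation on 30 records and completion instructions. Table 1 is visibly not exhaustive: tobacco use, which the SAMe-TT2R2 score needs, has no visible row. This also stands. The loss is therefore a risk if the form follows the table, and not a certainty. But Table 1 is the protocol's list of variables, and section 7.4.2 has the same gap.

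A reader might infer more than the documents support:

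- *That the composite cannot be built, or that pulmonary embolism belongs to no objective or analysis.* Parts of the objectives, outcome definitions and analysis are redacted, so only what is visible can be judged.
- *That pulmonary embolism was entered by mistake for systemic embolism.* It may be a deliberate extra event; the documents do not say. Nor do they say that it will be counted in the composite.
- *That recording pulmonary embolism contradicts the venous thromboembolism exclusion.* The exclusion concerns diagnoses before treatment or the index date. It shows how the plan classifies I26 and does not bar the event during follow-up.
- *That stroke/systemic embolism is the only visible effectiveness outcome.* The abstract also lists switch of treatment under effectiveness.

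**Conclusion.** The point holds as a mismatch between the variable table and the outcome that the plan defines and analyses. No visible Table 1 field captures systemic embolism or its date, and the only visible embolic outcome fields concern a non-overlapping diagnosis with no visible outcome definition or analysis.

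One of two components of the composite is affected. The number of events at risk is unknown. The conclusion assumes that the redacted rows do not hold the field, and its consequences assume that the collection form follows the visible table. The analysis is exploratory and descriptive, with no treatment comparison, and the I74 definition already exists. This is something that should be corrected before data collection; it does not undermine the primary objectives.

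**What to change.** Before abstraction starts:

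1. Confirm that Table 1 and the electronic case report contain *Systemic embolism (I74), yes/no* and *Time to systemic embolism (event date)*, or add them.
2. State that pulmonary embolism is not part of the stroke/systemic embolism composite. Keep it only as a separately defined descriptive event, or drop it.
3. Align the outcome list in section 7.4.2 with the abstract.

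The cost is at most two rows in Table 1, two fields in the form, and a sentence or two of text. The protocol is dated 10 October 2019 and collection is planned from 15 November 2019, with pilot validation of the form, so the change fits into work already planned. Made after abstraction, it could mean reopening the records of up to 7,500 patients (section 7.5).

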7. RESEARCH METHODS

7.1. Study Design

Observational, descriptive study of a retrospective cohort of adult patients diagnosed with NVAF in selected Health Maintenance Organization (HMO) of Colombia. These patients will be identified from the drug claim database, whose index date of the study will be the first prescription with any of the oral anticoagulants, that is, they are patients with NVAF for the first time starting a therapy with any of the NOACs between January 1, 2013 and June 30, 2018 and follow up period will be among January 2013 to July 2019, to ensure that the last patients can provide follow-up for one year. Patients will be required to have an NVAF diagnosis before or on the index date and health plan for 6 months pre-index date (baseline period).

Following, it will be verified that the patients meet the inclusion and exclusion criteria of the study. Once patients are selected and with the index date of each patient, they will be followed-up until discontinuation, switch of treatment, death or first event of stroke/ systemic embolism, major bleeding event, death or end of follow-up. Patients who are lost to follow-up, change of HMO and do not have access to the medical record will be considered as missing (Figure 1).

Figure 1. Study Design

[figure not shown]
The information will be analyzed in two moments: (i) the period of the index date, where the baseline information of patients will be collected; (ii) and the follow-up period, during this period the clinical results will be evaluated as well as the continuation of the treatment in the study population and for specific subpopulations.

Those patients who initiated treatment with any oral anticoagulant between January 2013 and June 30, 2018 will be included. This means that patients who start warfarin and NOACs would

be included within this period. Patients who initiate NOACs within the established period and who have been exposed to warfarin before 2013 will also be included.

Only the exposure period will be considered with the initial treatment, even in those patients who were on warfarin treatment before 2013, in the latter, the follow-up will be the treatment initiation with a NOAC in case of change after 2013. Follow-up will be carried out until the patient has a switch of treatment, discontinuation, death, first stroke/ systemic embolism, or major bleeding, or until end of follow-up, June 30, 2019 (Figure 2).

Figure 2. Inclusion of Patients

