7.2.1. Inclusion Criteria

Patients must meet all of the following inclusion criteria to be eligible for inclusion in the study:

- a) Patients with a diagnosis of AF considered according to the following diagnoses as per the ICD I48 codes at some point before or on the index date, without recorded valvular disease;
- b) Patients who have started treatment with apixaban, dabigatran, rivaroxaban and warfarin for the first time during the identification period, understanding as start of drug delivery by insurer, and after the diagnosis of AF between January 1, 2013 to June 30, 2018;
- c) Patients starting apixaban, dabigatran, rivaroxaban from January 1, 2013 to June 30, 2018 in patients previously exposed to warfarin;
- d) Patient had continuous health plan for 6 months pre-index date (baseline period);
- e) Patients older than 18 years old on the index date;
- f) NVAF diagnosis before or on the index date

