7.4.1. Claim Database

Claim databasee contains all prescriptions of all patients' medications chronologically. From this database, the index date will be established and the diagnosis of NVAF of the patient will be extracted. Similarly, this base will be used to assess the persistence on therapy and treatment patterns (duration of treatment, changes, persistence), pharmacy claim information, demographic information, diagnosis and insurance data.

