7.5. Study Size

The total population of patients treated with OAC between January 1, 2013 and June 30, 2018 was analyzed in the claim dabtabase. For the purpose of the study, it contains the information of 7,500 patients, once they were verified that they met the inclusion criteria of the study. This means that patients who start warfarin and NOACs would be included within this period. Patients who initiate NOACs within the established period and who have been exposed to warfarin before 2013 will also be included.

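### Prior warfarin use is read from claims alone with only six months of history guaranteed, so some experienced patients can be coded as unexposed and some continuing warfarin users can enter as new starters

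*Combined protocol and SAP*

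**What the plan says.** Section 7.3, Table 1, lists the item "Previously exposed to warfarin". The full row reads: "Previously exposed to warfarin Treatment Claim databases Yes, No". No look-back period is attached, and there is no category for unknown.

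Section 7.2.1, criterion b, admits patients who start an anticoagulant "for the first time during the identification period, understanding as start of drug delivery by insurer". Criterion c adds a second route for the NOACs only: "Patients starting apixaban, dabigatran, rivaroxaban from January 1, 2013 to June 30, 2018 in patients previously exposed to warfarin". Section 7.5 repeats that NOAC starters "who have been exposed to warfarin before 2013 will also be included".

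Criterion d sets the guaranteed history: "Patient had continuous health plan for 6 months pre-index date (baseline period". Section 7.4.1 says of the claims source: "From this database, the index date will be established and the diagnosis of NVAF of the patient will be extracted". The same section describes the database as holding every prescription in time order, but gives no start date.

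The medical record is abstracted for the same patients (sections 7.4.2 and 7.6.4). It supplies baseline characteristics, outcomes, concomitant drugs, INR values and the reason for a switch. It is not listed as a source for earlier anticoagulant use.

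**The concern.** A Yes/No item read from claims turns an absent claim into No. If the visible history is short, earlier warfarin can be missed, and the error runs towards labelling experienced patients as unexposed. Patients may also have visible histories of different lengths. The reported percentage of prior users would then depend partly on length of enrolment, and the plan does not ask for that length to be reported.

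The consequence differs by cohort:

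- **NOAC cohorts.** Eligibility is safe, because criterion c admits prior warfarin users. What can be wrong is the naive/experienced description, which is part of the primary objective on treatment patterns.
- **Warfarin cohort.** Criterion c does not cover warfarin, so entry depends on first-time status under criterion b. A patient already on warfarin, or returning to it, can look like a new starter. Section 7.3.1 counts persistence from the index date, so the count would begin mid-treatment in someone who may already be past the period of early discontinuation. Time to stroke/systemic embolism and to major bleeding would start from the same date.

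**Working it through.** The plan states no figure on this point. The 7,500 in section 7.5 is a count of available patients, so there is nothing to reproduce. Two checks were made.

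**1. How far back the guaranteed history reaches**

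Inputs: the identification period, 1 January 2013 to 30 June 2018 (66 months), and six months of enrolment before index (criterion d).

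- Index date 1 January 2013: history guaranteed from 1 July 2012.
- Index date 30 June 2018: history guaranteed from 30 December 2017.
- Six months reach back before 1 January 2013 only for index dates up to about 30 June 2013, which is the first 6 of the 66 months. For the other 66 - 6 = 60 months, the enrolment rule does not ensure that warfarin use before 2013 can be seen, although sections 7.1 and 7.5 name that use as a route of entry.
- For a patient indexed on the last day with minimum enrolment, about 60 of the 66 months, and all time before 2013, lie outside the guaranteed history.

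Six months is a minimum, so many patients may have more.

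**2. Illustration of the effect on the label**

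Let p be the true share with prior warfarin use and s the share of that use that claims capture. Both are assumptions; the documents give neither.

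- Reported share = p × s
- Experienced share among those labelled first-time = p(1 - s) / (1 - p × s)

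| p | s | Reported prior use | Experienced among labelled first-time |
|---|---|---|---|
| 20% | 90% | 18% | 0.02/0.82 = 2.4% |
| 30% | 75% | 22.5% | 0.075/0.775 = 9.7% |
| 40% | 60% | 24% | 0.16/0.76 = 21.1% |

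With wider assumptions (p from 10% to 50%, s from 50% to 95%) the last column runs from 0.005/0.905 = 0.6% to 0.25/0.75 = 33%. The width of that range shows how little the documents settle.

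These figures illustrate the label in NOAC starters. They do not estimate how many continuing users would enter the warfarin cohort, and the documents offer no basis for such an estimate.

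**3. What the plan does about missing history**

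Section 7.1 recognises movement between insurers, but in the context of follow-up: "Patients who are lost to follow-up, change of HMO and do not have access to the medical record will be considered as missing". Section 7.9 notes that claims cannot show whether a drug was taken as prescribed. It does not mention earlier use that claims cannot show.

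**The case against.** The strongest reply is that the claims history may be much better than six months. Section 7.4.1 describes the database as complete and chronological. The abstract and section 7.1 describe a cohort drawn from selected HMOs, and the abstract uses the plural, so a patient who moves between covered insurers may stay visible. The plan evidently expects to recognise warfarin use before 2013. It also states openly that first-time use means first delivery by the insurer, so a patient with older use elsewhere meets the written criterion. All of this stands. It lowers the likely size but does not close the gap. No start date is stated, and nothing shows that drug supplied before enrolment or by an insurer outside the database is captured.

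A reader might infer more than the documents support:

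- **That history beyond six months, or under another insurer, is necessarily invisible.** The documents do not say so.
- **That NOAC eligibility is compromised.** Criterion c rules this out.
- **That planned estimates for first-time users are contaminated.** Section 7.7 names no analysis of first-time against experienced patients, only unspecified clinically relevant subgroups.
- **That comparisons between drugs are biased.** Section 7.7 says treatments will not be compared, and nothing shows that drugs started later have longer visible histories.

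The chart is not a perfect remedy either. Access depends on HMO authorisation (section 7.2), section 7.9 warns that abstractors may rely on indirect information, and the drug items now taken from the chart do not include prior anticoagulant history. Under section 7.6.4 collection begins after eligibility is checked, so re-testing criterion b from charts before entry would reverse the planned order of work. The fix is shaped accordingly.

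**Conclusion.** The concern holds in a limited form. With claims as the only source, six months as the only guaranteed history and no stated database start date, some warfarin-experienced patients can be coded No. For NOAC starters the effect is confined to a descriptive label. For the warfarin cohort, some continuing users or re-starters could be counted as new starters, with persistence and time to event measured from the wrong point in treatment.

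The documents do not allow the size to be determined. The range of 2.4% to 21.1% rests wholly on assumed prior use of 20-40% and assumed capture of 60-90%. It shows that the effect could be trivial or material, not that it is either. The change is worth making because the charts are being read anyway and a second source can recover exposures that claims miss.

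**What to change.** - **Table 1:** change the source for prior warfarin use to claim databases and medical record. Code Yes if either documents warfarin before the index date, and record which source showed it.
- **Warfarin cohort:** keep the claims-based entry rule, so that the order of work in section 7.6.4 is unchanged. Flag starters whose chart shows earlier warfarin, and report persistence and time to event with and without them.
- **Look-back:** report the length of claims history before index for each patient, and give a sensitivity result in patients with longer history, for example at least 12 months. Cutting everyone to a fixed six months would equalise look-back but discard known history and worsen the under-capture.
- **Section 7.9:** add that earlier use seen by neither source will still be coded No.

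Cost: one extra field in an abstraction already planned, some false positives from indirect chart information (the recorded source lets these be examined), and a slightly smaller warfarin set in the sensitivity analysis.
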